- 6. von Ungern-Sternberg, Effect of obesity and site of surgery on perioperative lung volumes. British Journal of Anaesthesia , Volume 92 , Issue 2 , 202 207.
- 7. https://clinicaltrials.gov/ct2/show/NCT02865083?term=pannus+retraction&rank=1

B3. DESCRIPTION OF RESEARCH PROTOCOL A. Study Design – Overview, Methods, Procedures

Overview

To determine whether the traxi® device warrants incorporation into routine practice, we will conduct an open-label, randomized, controlled trial to evaluate the use of traxi for obese patients undergoing non-urgent cesarean delivery. We will examine operative time, cardiopulmonary function, and patient/provider satisfaction.

Methods

Enrollment/randomization

Screening, recruitment, and enrollment of participants will occur in the obstetrical clinics and on Labor and Delivery at Brigham and Woman's Hospital (BWH), Beth Israel Deaconess Medical Center (BIDMC) and at Massachusetts General Hospital (MGH). Possible eligible patients may be handed a brochure about the study by their OBGYN provider at BIDMC so they can decide make an informed choice about participating. We will review the medical record of potentially eligible patients to confirm eligibility. At the time we approach each patient, we will review the eligibility criteria with the patient to further ensure eligibility. A script is available for the consenter. Specifically, consistent with standard medical care, we will confirm with patients that they do not have a history of allergic reaction to adhesives, such as those used in medical tape.

Participants who meet eligibility criteria and provide written, informed consent will be randomized to the traxi arm or standard of care (control) arm. We will use computer-generated block randomization to randomize participants in a 1:1 ratio to the traxi arm or the control arm. Randomization will be stratified by whether the patient has a history of cesarean delivery / open abdominal surgery versus no history of cesarean delivery / open abdominal surgery versus no history of cesarean delivery.

Study procedures

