After the participant is in the operating room and before the cesarean delivery, we will use a spirometer to measure forced vital capacity, forced expiratory volume, vital capacity and tidal volume. We will perform these measurements while the participant is in the supine position both before any retraction has occurred and after the traxi device or standard method for panniculus retraction has been applied.

After the cesarean delivery is complete, we will assess provider satisfaction by administering a brief questionnaire developed by our research team. The survey will be distributed to personnel involved in

the delivery either on paper or via REDCap.

We will assess participant satisfaction via a survey that will be available either on paper or via REDCap.

We will conduct a medical record review to collect data on the secondary outcomes below that are not available via spirometry or questionnaire.

Outcomes

The primary outcome will be total operative time, time from incision to closure.

Secondary outcomes will include:

- Spirometry: forced vital capacity, forced expiratory volume, vital capacity and tidal volume
- Provider satisfaction
- Participant satisfaction
- Intraoperative data, such as estimated blood loss and number of scrubbed personnel
- Neonatal outcomes, such as Apgar score and NICU admission
- Length of stay postoperatively,
- Maternal complications, such as need for re-admission and wound disruption or infection.

B. Statistical Considerations

Sample Size Justification: Our sample size calculation is based on data from a prior study that reported total operative time (incision to closure) by BMI [7]. In that study, for patients with a BMI \geq 40 the mean total operative time was 55.0 minutes (±26 minutes). We hypothesize that the operative time in the control arm will be similar to that in the prior study and that the mean operative time in the traxi arm will be 45 minutes (±10 minutes). Using a two-sided alpha of 0.05, in order to achieve 85% power to detect the specified difference we will need 102 participants per arm. To allow for 15% loss to follow-up, we will aim to enroll 120 participants per arm.

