We hypothesize that participants will have a baseline forced vital capacity of 2.0L and that after retraction the forced vital capacity will drop by 0.1L to 1.9L in the control am. Assuming a two-sided alpha of 0.05, we will have more than 85% power to detect a difference between the 0.1L decrease in the control arm and a 0.19 L decrease in the traxi arm (assuming a standard deviation of the difference of 0.2L).

Data Analysis: We will employ an intention-to-treat approach for the data analysis. Descriptive data will be presented as a proportion, mean with standard deviation or median with interquartile range. Comparisons will be made using Chi-square or Fisher's exact test for categorical variables and parametric or non-parametric tests for continuous variables based on data distribution.

We will use linear regression to estimate beta and 95% confidence intervals for difference in the primary outcome, time from incision to closure, between the traxi and control arms. While we anticipate that randomization will balance the distribution of measured and unmeasured potential confounders in the two study arms, if this is not the case, we will assess the influence of potential confounders as needed. We will use a similar analytic approach for the secondary outcomes, which also are continuous. All data will be analyzed with SAS 9.4 (SAS Institute Inc., Cary, NC, USA). All tests will be two sided and a P value <0.05 will be required to confer significance.

Release of Data

Data from study participants enrolled at BWH and MGH will be sent to BIDMC, the coordinating site. A data use agreement will be executed to facilitate data transfer. Data will be sent via secure data transfer.

The PI will create a research steering committee that includes the PI and at least one other coinvestigator. All requests to use data from the study must be made in writing and will be reviewed by the steering committee. Release of data may occur after appropriate data use agreements have been enacted.

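### The primary regression does not name the factor that stratified the randomisation; if that factor predicts operative time, the reported confidence interval is slightly too wide

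*Combined protocol and SAP*

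**What the plan says.** Section B3.A (Enrollment/randomization) describes the allocation: "We will use computer-generated block randomization to randomize participants in a 1:1 ratio to the traxi arm or the control arm". It continues: "Randomization will be stratified by whether the patient has a history of cesarean delivery / open abdominal surgery", followed directly by "versus no history of cesarean delivery / open abdominal surgery versus no history of cesarean delivery". As printed, the factor could have two levels or three, although a repeated phrase is the likelier explanation.

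Section B3.A (Outcomes) sets the endpoint: "The primary outcome will be total operative time, time from incision to closure". Section B3.B (Data Analysis) sets the model: "We will use linear regression to estimate beta and 95% confidence intervals for difference in the primary outcome, time from incision to closure", comparing the two arms. No covariate is listed. The only text on adjustment follows a statement that randomisation is expected to balance confounders: "if this is not the case, we will assess the influence of potential confounders as needed". Nothing elsewhere in the document puts the stratification factor into the model. The same section carries a similar approach over to the secondary outcomes.

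**The concern.** Stratified blocks remove chance imbalance in the stratification factor, so the treatment estimate no longer varies because of it. A regression on arm alone does not use this. It leaves the variation between strata in the residual and computes its standard error as if allocation had been unstratified. If the factor is prognostic, the reported standard error exceeds the true one, the 95% interval covers more than 95%, and the test rejects less often than its nominal level.

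The conditional clause is a poor safeguard here. Imbalance triggers it, and this is the factor least likely to be imbalanced.

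The clause also leaves a choice open. It names no candidate confounders and no threshold. It does not say whether an adjusted estimate would replace the primary result or only support it. In an open-label trial that should be settled before outcome data are seen.

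**Working it through.** **Inputs from section B3.B (Sample Size Justification).** Control mean 55 min, SD 26; traxi mean 45 min, SD 10; two-sided alpha 0.05; 102 per arm analysed; 120 per arm enrolled.

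**Assumed, because the documents do not give them.** Two strata, with share p in one of them; a difference d in mean operative time between strata, the same in both arms; the block size.

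**The plan's own figure.** The mean variance is (26² + 10²)/2 = 388, so the root-mean-square SD is 19.7. The required size is n = 2 × (1.960 + 1.036)² × 388/10² ≈ 70 per arm for 85% power, not 102. With 102 per arm, SE = √(776/102) = 2.76 min and power = Φ(10/2.76 − 1.96) ≈ 95%. The allowance for loss does reproduce: 102/0.85 = 120. The mismatch in n is a separate matter. It explains why the powers below are near 95% rather than 85%.

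**Effect on the standard error.** The variance between strata is p(1−p)d². There are two ways to read the SDs of 26 and 10.

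*Reading A: they are SDs within strata.* Reported over true SE = √(1 + p(1−p)d²/388). With p = 0.5:
- d = 5: √(1 + 6.25/388) = 1.008
- d = 10: √(1 + 25/388) = 1.032
- d = 15: √(1 + 56.25/388) = 1.070

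Simulation of 40,000 trials per setting, arm alone versus arm plus stratum:

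| d (min) | Mean CI width (min) | Type I error, arm alone | Power |
|---|---|---|---|
| 5 | 10.94 vs 10.86 | 5.1% | 94.6% vs 94.8% |
| 10 | 11.20 vs 10.86 | 4.4% | 94.2% vs 94.9% |
| 15 | 11.62 vs 10.86 | 3.6% | 93.3% vs 94.9% |

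With the stratum in the model, type I error was 5.1% to 5.3%. The actual SD of the estimate was about 2.77 min under both models, so only the reported precision differs. With a 70/30 split the power gains were 0.2, 0.5 and 1.5 points.

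*Reading B: they are total SDs that already contain the stratum effect.* Let R² = p(1−p)d²/388 and r = √(1−R²). Then reported over true SE = 1/r, and type I error for arm alone = 2Φ(−1.96/r). Power is Φ((3.63 − 1.96)/r) for arm alone and Φ(3.63/r − 1.96) for arm plus stratum, where 3.63 = 10/2.76. With p = 0.5:

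| d (min) | R² | SE ratio | Type I error, arm alone | Power |
|---|---|---|---|---|
| 5 | 0.016 | 1.008 | 4.8% | 95.3% vs 95.5% |
| 10 | 0.064 | 1.034 | 4.3% | 95.7% vs 96.3% |
| 15 | 0.145 | 1.081 | 3.4% | 96.4% vs 97.5% |

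A separate simulation under reading B used blocks of 4, p = 0.6 and a common SD of 19.7. At d = 10 the mean reported SE was 2.755 for arm alone, against an actual SD of 2.669; the adjusted SE was 2.668. At d = 0 the two models agreed.

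**Would the imbalance clause bring the factor in?** The check simulated 240 enrolled, stratified blocks of 4 or 8, 15% random loss and a stratum share of 50% or 70%. The share differed between arms at chi-square p < 0.05 in 0 of 5,000 trials in each setting. In 95% of trials the arms differed by at most 5.7 percentage points.

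**The case against.** The strongest reply is that this is a small efficiency point that errs in the safe direction. The estimate is unbiased, no false positive is risked, and power stays above the planned 85% under either model. The size depends on a stratum difference that the documents do not give; at 5 minutes the effect is negligible. The plan's own SDs also argue against large values. With two equal strata, a 15-minute difference would take 56.25 of the 100 units of variance in the traxi arm if 10 is the total SD, and 20 minutes would take all of it. The fall in arm-alone power under reading A comes from adding stratum variance to the stated SDs; under reading B that power rises. The plan leaves its covariates unstated rather than excluding this one. The imbalance check used a chi-square trigger that the plan does not contain.

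All of this stands as a limit on size, and it is why the effect is called mild. It does not remove the mismatch. The SE ratio exceeds 1 under both readings whenever the factor is prognostic, and choosing a factor for stratification suggests that it was thought to be. Leaving covariates open is itself the gap. A looser trigger would still act on imbalance, which the design suppresses for this factor.

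**Conclusion.** The point holds and is worth correcting, but its effect is modest. The randomisation is stratified, the primary model does not name the stratification factor, and the conditional clause would rarely supply it. For assumed stratum differences of 5 to 15 minutes and two equal strata, the reported SE is about 1% to 8% too large across the two readings of the SDs. Type I error for the arm-only model runs from no detectable change down to about 3.4%, and the power forgone is roughly 0.1 to 1.5 points. If the factor does not predict operative time, nothing is lost. There is no bias and no inflation of alpha. The undefined status of an imbalance-driven adjusted estimate is a further reason to fix the model in advance.

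**What to change.** 1. In section B3.A, state the levels of the stratification factor unambiguously.
2. In section B3.B, specify the primary model as linear regression of operative time on arm and randomisation stratum, as randomised. Label the unadjusted difference, and any adjustment prompted by observed imbalance, as sensitivity analyses.
3. Include the stratum in the models for the continuous secondary outcomes.

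Site and BMI may be pre-specified as further covariates, but this point does not require them.

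The cost is about two sentences. The stratum is recorded at randomisation, so no data are added. The model uses one degree of freedom for two levels, or two for three levels, out of roughly 200.

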Investigators can request to use 1) data that contain elements of a limited dataset or 2) data that are completely de-identified. Investigators who wish to obtain data that contain elements of a limited dataset first must obtain approval from the steering committee and then will have to obtain appropriate approval from the BIDMC Committee on Clinical Investigations (CCI) and from their own institution. After obtaining approval, data may be given to the researchers. Investigators who wish to receive completely de-identified data may do so after approval by the steering committee and after signing a letter indicating that they will not attempt to obtain the identity of any of the participants. A data use agreement or material transfer agreement will be executed as needed.

C. Subject Selection

Inclusion criteria for patients

- Pregnant
- Age 18-50 years
- BMI greater than or equal to 40 kg/m²
- Undergoing non-emergent cesarean delivery
- Able and willing to provide written, informed consent
- Singleton gestation

Inclusion criteria for providers

- Listed as a provider_on the patient's delivery summary
- May include nurse, resident, attending, medical student, anesthesiologist, physician's assistant, surgical technician

Exclusion criteria for patients

- Fetal demise
- Disruption of abdominal skin, such as due to infection, rash, abrasion or laceration
- Known adhesive allergy

B4. POSSIBLE BENEFITS

We do not know whether participants in the study will gain any direct benefit from participation. However, we hope that this study will provide data to inform how we can improve care for future patients. It is possible that participants who are randomized to the intervention arm of this study will have a better delivery experience due to increased preservation of dignity. It also is possible that providers will benefit by improving retraction capability and thus visualization while operating and operative efficiency.

B5. POSSIBLE RISKS AND ANALYSIS OF RISK/BENEFIT RATIO

There are very few anticipated risks involved in this study. Patients with an allergy to adhesives may experience a contact dermatitis allergic reaction to the adhesive of the traxi device or the medical tape.

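### The primary operative-time model prespecifies no covariates and adjusts only after observed imbalance, which forgoes a modest gain in precision and leaves the choice of model open

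*Combined protocol and SAP*

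**What the plan says.** Section B3.B (Data Analysis) plans a linear regression for the between-arm difference in the primary outcome, time from incision to closure, and names no covariate. It expects randomization to balance potential confounders, then adds: "if this is not the case, we will assess the influence of potential confounders as needed". No candidate variables are listed, imbalance is not defined, and nothing says whether an adjusted result would replace or accompany the unadjusted one. Significance is judged at a two-sided P below 0.05.

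Three other places bear on this:

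- **Randomization (B3.A, Enrollment/randomization).** Allocation is 1:1 in blocks, stratified by history of cesarean or open abdominal surgery. It is not stratified by BMI. The stratification factor does not reappear in the analysis section.
- **Sample size (B3.B).** The inputs come from "data from a prior study that reported total operative time (incision to closure) by BMI". Only the figure for BMI 40 and over is given. The calculation takes no credit for covariate adjustment.
- **Eligibility (B3.C).** Patients need a "BMI greater than or equal to 40" kg/m², with no upper limit, so BMI must be known for everyone enrolled.

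**The concern.** In a randomized trial, adjusting for a prognostic baseline variable removes outcome variance whether or not the arms differ on it. An imbalance trigger therefore asks the wrong question. In most trials the arms will look balanced, the trigger will not fire, and the gain goes unused.

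The clause also leaves more than one primary P value available in an open-label trial, with no rule for choosing between them.

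Finally, the design balances the arms on surgical history, but the analysis does not use that factor. If it predicts operative time, a model that leaves it out tends to overstate the standard error.

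At stake are a modest amount of precision and a clear statement of which result is the trial's answer.

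**Working it through.** **Inputs from B3.B:** control 55 minutes (SD 26), traxi 45 minutes (SD 10), difference 10, two-sided alpha 0.05, 85% power, 102 per arm.

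**Assumed, not in the documents:** BMI explains R² = 2%, 5% or 10% of the within-arm variance of operative time among patients with BMI 40 and over.

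**1. The plan's own figure.** The root-mean-square SD is √[(26² + 10²)/2] = 19.70.
- n per arm = 2 × [19.70 × (1.960 + 1.036)/10]² = 69.7, so 70. The plan says "we will need 102 participants per arm".
- With SD 26 in both arms the same formula gives 121.4, so 122.
- The dropout step does reproduce: 102/0.85 = 120.

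The figure of 102 therefore does not follow from the stated inputs at 85% power. That is a separate matter, but it means 85% cannot serve as the baseline here. Power at 102 per arm is instead computed from the stated SDs, and again with SD 26 in both arms.

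**2. Unadjusted baseline at 102 per arm.** SE = SD × √(2/102); power = Φ(10/SE − 1.96).
- SDs 26 and 10: SE = 2.76 minutes, power 95.2%.
- SD 26 in both arms: SE = 3.64 minutes, power 78.4%.

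**3. With BMI always in the model.** The SE is multiplied by √(1 − R²). The equivalent increase in sample size is 1/(1 − R²) − 1.

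| R² | SE reduction | Equivalent extra patients | SE and power, SDs 26 and 10 | SE and power, SD 26 in both |
|---|---|---|---|---|
| 0 | – | – | 2.76 min, 95.2% | 3.64 min, 78.4% |
| 2% | 1.0% | 2% | 2.73 min, 95.6% | 3.60 min, 79.2% |
| 5% | 2.5% | 5% | 2.69 min, 96.1% | 3.55 min, 80.5% |
| 10% | 5.1% | 11% | 2.62 min, 96.9% | 3.45 min, 82.5% |

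The gain is 0.4 to 1.7 percentage points on the stated SDs, and 0.8 to 4.1 points if the SD is 26 in both arms.

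**4. Type I error.** This was simulated with 102 per arm, one covariate and R² of 2–10%.
- Always reporting the smaller of the adjusted and unadjusted P values gave about 5.7% to 6.5%.
- Applying a fixed trigger mechanically (adjust only if the arms differ on BMI at P < 0.05) stayed close to 5%, and no higher than 5.3%.

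Any inflation thus comes from the undefined choice between results, not from the trigger as such.

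**5. Stratification factor.** The documents give no figure for how surgical history relates to operative time, so its contribution cannot be quantified. The case for including it rests on the design.

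**The case against.** The strongest defence is that an unadjusted comparison in a randomized trial is unbiased, and its confidence interval already allows for chance imbalance. The clause speaks only of assessing influence, which can be read as a supportive check and not as a replacement for the primary result. The benefit of adjustment rests on an R² the documents do not supply. All of this stands, and it limits the size of the point. It does not justify making adjustment depend on observed balance, or leaving the status of the adjusted result unstated.

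A reader might also infer any of these stronger claims, none of which the documents support:

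- **That precision already paid for is being lost.** Randomization is not stratified by BMI and the sample size takes no credit for adjustment, so an optional gain is forgone. The phrase comes closer to fitting the stratification factor, but the sample size takes no credit for that either.
- **That the plan treats BMI as a driver of operative time in this population.** Aim 1 compares obese with non-obese patients, and the sizing source contributes one figure for BMI 40 and over. No relation is stated within the enrolled range, and restricting the range usually weakens a correlation.
- **That control of the 5% error rate is compromised.** The plan does not say the smaller P value will be reported; 5.7–6.5% describes a worst case.

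**Conclusion.** The point holds as an inexpensive improvement to the analysis, not as a flaw that invalidates it. The covariate rule is tied to the wrong condition, its content is left open, and the stratification factor is missing from the model.

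The size is modest. On the assumed R² range, the standard error falls by a few percent and power at 102 per arm rises by less than two points on the stated SDs. It matters more, by up to about four points, if the traxi arm proves as variable as the control arm. These figures use a normal approximation and the same proportional variance reduction in both arms. The true R² may lie near or below the low end of the range.

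**What to change.** In B3.B (Data Analysis), state that the primary analysis is a linear regression of incision-to-closure time on arm, the randomization stratification factor (history of cesarean or open abdominal surgery) and BMI as a continuous covariate taken at one fixed measurement time, whatever the observed balance. Delete the imbalance-triggered sentence. Label the unadjusted comparison and any other covariate model as sensitivity analyses.

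The cost is a few sentences, settled before outcome data are examined by arm. Both covariates must already be known, BMI for eligibility and surgical history for randomization, so no extra patients or data collection are needed.

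### Provider satisfaction can yield several replies per randomized delivery, but the plan does not state the unit of analysis

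*Combined protocol and SAP*

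**What the plan says.** Randomization is by patient. B3.A (Enrollment/randomization) will "randomize participants in a 1:1 ratio to the traxi arm or the control arm", so each randomized unit is one delivery.

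Provider satisfaction is a listed secondary outcome (B3.A, Outcomes) and one of the two parts of Aim 3 (B1). B3.A (Study procedures) measures it with "a brief questionnaire developed by our research team", and adds: "The survey will be distributed to personnel involved in" the delivery. B3.C sets no limit on respondents per delivery. It lists seven role types, beginning "May include nurse, resident, attending, medical student, anesthesiologist". B6 says that providers are found from the delivery summary and emailed, and that replying is voluntary.

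The only analysis text is B3.B, Data Analysis. For operative time: "We will use linear regression to estimate beta and 95% confidence intervals for difference in the primary outcome". For the rest: "We will use a similar analytic approach for the secondary outcomes, which also are continuous". It also gives general rules: "Comparisons will be made using Chi-square or Fisher's exact test for categorical variables", and "parametric or non-parametric tests for continuous variables based on data distribution". All tests are two-sided at 0.05. Nothing defines a provider score per delivery, a designated respondent, a mixed model, GEE or clustered standard errors. The documents do not say that a survey carries a delivery identifier.

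**The concern.** Staff at one delivery rate the same operation on the same patient. Aim 3 expects satisfaction to improve through visualization and ease of delivery, which the whole team shares, so positive correlation between their replies is plausible.

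Operative time has one value per delivery, so ordinary regression suits it. Carried over to surveys entered one per row, the same regression counts every reply as independent information. The standard error is then too small, and a benefit of the device on provider experience could be declared more often than the stated 5% allows. In an open-label trial meant to inform routine use, that would matter for a stated aim.

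**Working it through.** **Plan's own figure.** There is none to reproduce: no power or sample size is given for provider satisfaction. The 102 participants per arm from the primary sample size is used below only as the number of deliveries. The error formula does not depend on it.

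**Assumed inputs.** Replies per delivery (m) and within-delivery correlation (ICC). Neither is in the documents.

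**Formulas.**
- Design effect: DE = 1 + (m − 1) × ICC.
- True two-sided error with one row per survey: 2 × [1 − Φ(1.96/√DE)].
- 95% CI half-width in SD units at 102 deliveries per arm: 1.96 × √(2/(102m)), multiplied by √DE when corrected.

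| m | ICC | DE | √DE | Type I error | CI coverage | Half-width, uncorrected → corrected |
|---|---|---|---|---|---|---|
| 1 | any | 1 | 1 | 5.0% | 95.0% | unchanged |
| any | 0 | 1 | 1 | 5.0% | 95.0% | unchanged |
| 2 | 0.05 | 1.05 | 1.02 | 5.6% | 94.4% | 0.194 → 0.199 |
| 3 | 0.1 | 1.2 | 1.10 | 7.4% | 92.6% | not needed here |
| 4 | 0.3 | 1.9 | 1.38 | 15.5% | 84.5% | 0.137 → 0.189 |

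Example for the last row: DE = 1 + 3 × 0.3 = 1.9; 1.96/1.38 = 1.42; 2 × [1 − Φ(1.42)] = 0.155. The 102 × 4 = 408 replies per arm carry the information of 408/1.9 ≈ 215.

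**Check by simulation** (no true effect, 102 deliveries per arm, 10,000 runs per case, Monte Carlo SE about 0.2 points at 5%). Row-per-survey regression on a continuous score gave 5.4%, 7.8% and 15.4% for the last three rows. With standard errors clustered on delivery it gave 4.9%, 5.3% and 5.1%. A t-test on per-delivery means (5,000 runs, four cases with m from 3 to 5 and ICC from 0.1 to 0.5) gave 5.0% to 5.3%. The plan's other tests do not avoid the problem: on an assumed 5-point item at m=4, ICC 0.3, the rank test gave 14.4% and Chi-square on the top two categories 11.7%.

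**Limit of clustering.** B2 presents the device as cutting the number of additional staff needed, so the mix of respondents could differ by arm. Assumed case: ICC 0.3, three replies per delivery, plus one role that scores 0.5 SD lower and replies in every control delivery but only half of the traxi deliveries.
- Mean shift in the control arm: 0.5/4 = 0.125 SD.
- Mean shift in the traxi arm: (0.5 × 0.5)/3.5 = 0.071 SD.
- Spurious difference: 0.125 − 0.071 = 0.054 SD in favour of traxi.

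Simulated error with clustered standard errors was 8.6% without role in the model and 5.4% with it. With the role 0.25 SD lower, it was 5.7% and 5.0%. A per-delivery mean does not remove this bias: a 4,000-run simulation of the 0.5 SD case gave 9.4%.

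**The case against.** The strongest reply is that the plan never says each survey is a row. It says *similar* to the primary analysis, which has one value per delivery, so averaging the replies within each delivery would comply and would remove the within-delivery problem. That stands. A reader might infer that a faulty analysis is planned, or that the error will be 15.5%. The documents support neither. They leave the unit open, and both m and ICC are assumptions that include cases with little or no inflation. The gap still matters, because either choice complies with B3.B and could be made after the data are seen.

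The outcome is also secondary and unpowered, and replies are voluntary, so m may be low. This limits the importance of the point but does not remove it, since the outcome will still be tested at 0.05.

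The same staff may rate several deliveries, and the plan is silent on that too. Because arm is assigned by delivery, this need not defeat a delivery-level analysis. With 60 or 20 staff working across both arms (assumed provider ICC 0.2, delivery ICC 0.3, m=4), simulated delivery-level error was 5.6% and 4.9% (Monte Carlo SE about 0.4 points), against 16.9% and 15.6% by row.

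A reader might also infer from the clause calling the secondary outcomes continuous that NICU admission, re-admission and wound outcomes will get linear regression. B3.B already assigns categorical variables Chi-square or Fisher's exact test, so this is a wording slip with negligible effect.

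**Conclusion.** The point holds as an unspecified unit of analysis for one secondary outcome, for which the named methods are not valid if applied to the surveys as collected. Inflation needs two conditions together: one row per survey, and positive correlation within a delivery. If both hold, the error under the assumed values runs from 5.6% (negligible) to 15.5%. If either fails, there is none.

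Participant satisfaction, with one report per randomized patient, is not affected. Nor are operative time and the sample size.

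Treating the delivery as the unit restores about 5% only if the mix of respondents does not differ by arm. Otherwise a bias remains that no standard-error correction removes. This is a cheap improvement worth making, not a threat to the trial's main conclusion.

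**What to change.** Add to B3.B, Data Analysis, that provider satisfaction will be analysed with the delivery as the unit, by one of two equally acceptable routes, chosen in advance:

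- one pre-defined score per delivery, for example the mean of the replies; or
- a model of individual replies with standard errors clustered on delivery (GEE, with a link suited to the item type).

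Record a delivery ID and the provider's role on each survey. Without the ID, replies cannot be grouped by delivery later. Include a role-adjusted analysis of the individual replies, with clustered standard errors, to address a respondent mix that differs by arm.

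Do not simply delete the clause about continuous outcomes: that would leave the linear-regression approach applying to binary outcomes as well. If it is edited, limit the sentence to *the continuous secondary outcomes*.

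Cost: a sentence or two in the plan, a standard SAS procedure and two survey fields. The interval for this outcome becomes wider but correct: about 1.4 times at m=4, ICC 0.3 (0.137 to 0.189 SD), almost unchanged at m=2, ICC 0.05, and unchanged at m=1.
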